13.2.12 SYMPTOM ASSESSMENT IN DRY EYE (SANDE)

The SANDE Questionnaire will be assessed on both eyes at all visits. Visit 1 and 5 assessments will be pre-CAE®. In this questionnaire, subjects indicate the frequency that their eyes feel dry and/or irritated and the severity of their symptoms. Frequency is measured on a 0-100 mm scale with 0 indicating rarely and 100 indicating all the time. Severity is also measured on a 0-100 mm scale with 0 indicating very mild and 100 indicating very severe. The SANDE Score is calculated as the product of the square root of the Frequency Score and the square root of the Severity Score.

The Frequency, Severity and combined SANDE Scores will be summarized by treatment group and visit using quantitative summary statistics. Change from baseline will be also summarized.

Pairwise two-sample t-tests will be employed to compare treatment and vehicle means at each visit and time point. The differences in means, two-sided 95% CIs for the difference in means and p-values will be reported. Wilcoxon rank sum tests will also be conducted. Analyses will be performed on the mITT population with observed data only.

Changes from baseline will be compared between treatment groups using ANCOVA models that adjust for baseline value, baseline inferior corneal staining (Ora Calibra® scale) and baseline eye dryness

(VAS). The differences in means, two-sided 95% CIs for the difference in means and p-values will be reported. T-tests and Wilcoxon rank sum tests will also be conducted. Analyses will be performed on the mITT population with observed data only.

14. Exploratory Analyses

No exploratory analyses are planned.

15. Subgroup Analyses

Patients will be stratified by the Pre-CAE® ICCS (i.e., ≤ 1.5 or > 1.5) according to the Ora Calibra® staining scale and eye dryness score (i.e., < 60 or ≥ 60) in the study eye.

Subgroup analyses are planned for the 4 groups defined by the 2 stratification factors (Pre-CAE®):

1. ICCS ≤ 1.5 according to the Ora Calibra® staining scale and eye dryness score < 60
2. ICCS ≤ 1.5 according to the Ora Calibra® staining scale and eye dryness score ≥ 60
3. ICCS > 1.5 according to the Ora Calibra® staining scale and eye dryness score < 60
4. ICCS > 1.5 according to the Ora Calibra® staining scale and eye dryness score ≥ 60 .

Subgroup analyses will be conducted for corneal fluorescein staining (Ora Calibra® scale), corneal fluorescein staining (Oxford scale), VAS, and Total OSDI. Each endpoint will be summarized by subgroup, treatment group, visit and time point (where appropriate).

Additional subgroup analyses will be conducted based upon strata defined by median baseline values in pre-CAE assessments. For each endpoint, separate analyses will be conducted for patients with pre-CAE baseline scores \leq the pre-CAE baseline median, and for patients with pre-CAE baseline scores $>$ the pre-CAE baseline median. These subgroup analyses will be conducted for all efficacy endpoints.

Subgroup analyses of symptom endpoints will also be conducted for the following two groups:

1. Patients with time to CAE qualification ≤ 20 minutes
2. Patients with time to CAE qualification > 20 minutes

For each subgroup, pairwise two-sample t-tests will be employed to compare treatment and vehicle means at each visit and time point. The differences in means, two-sided 95% CIs for the difference in means and p-values will be reported. Wilcoxon rank sum tests will also be conducted. Analyses will be performed on the mITT population with observed data only.

Changes from baseline will be compared between treatment groups using ANCOVA models that adjust for baseline value. The differences in means, two-sided 95% CIs for the difference in means and p-values will be reported. T-tests and Wilcoxon rank sum tests will also be conducted. Analyses will be performed on the mITT population with observed data only.

16. Safety Analyses

All safety analyses will be conducted using the Safety Population.

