12.4.9 Sub-Group Analyses

Patients will be stratified by the Pre-CAE® inferior corneal staining score (ICCS) (i.e., ≤ 1.5 or > 1.5) according to the Ora Calibra® staining scale and eye dryness score (i.e., < 60 or ≥ 60) in the study eye.

Subgroup analyses are planned for the 4 groups defined by the 2 stratification factors (Pre-CAE®):

1. inferior corneal staining score (ICCS) ≤ 1.5 according to the Ora Calibra® staining scale and eye dryness score < 60
2. inferior corneal staining score (ICCS) ≤ 1.5 according to the Ora Calibra® staining scale and eye dryness score ≥ 60
3. inferior corneal staining score (ICCS) > 1.5 according to the Ora Calibra® staining scale and eye dryness score < 60
4. inferior corneal staining score (ICCS) > 1.5 according to the Ora Calibra® staining scale and eye dryness score ≥ 60.

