13.1.1 PRE-CAE[®] INFERIOR FLUORESCEIN STAINING (ORA CALIBRA[®] SCALE)

Pre-CAE[®] fluorescein staining in the inferior region of the cornea will be graded using the Ora Calibra[®] Corneal and Conjunctival Staining Scale. The Ora Calibra[®] Corneal and Conjunctival Staining Scale ranges from 0 to 4 (half grade increments may be used), where grade 0 = none, 1 = trace, 2 = mild, 3 = moderate, and 4 = severe.

Changes from baseline in the pre-CAE[®] inferior fluorescein staining scores will be summarized at Visit 5 (Day 85 ± 2) by treatment group for the study eye using quantitative summary statistics. Changes from baseline will be compared between each AXR-159 Ophthalmic Solution group versus vehicle group at matched dosing frequency (TID or BID) using an ANCOVA model that adjusts for baseline. Specifically, the ANCOVA model will include terms for baseline inferior corneal staining score (ICCS) and baseline eye dryness score as covariates and treatment group as a factor in the model. The differences in means, two-sided 95% CIs for the difference in means and p-values will be reported. Pairwise t-tests from the ANCOVA model will be used to compare treatment and vehicle groups.

The following SAS code will be used to run the ANCOVA analysis for each of Stage 1 and Stage 2:

```
PROC MIXED DATA = INDATA;
```

```

CLASS TREATMENT;
MODEL CHANGE_ICSS = BASELINE_ICSS BASELINE_EDS TREATMENT
   / SOLUTION COVB;
LSMEANS TREATMENT / CL PDIFF;
ODS OUTPUT LSMEANS = OUTLS DIFFS = OUTDIFFS;
RUN;

```

where

- *TREATMENT* is the name of the treatment group variable
- *BASELINE_ICSS* is the baseline pre-CAE® inferior fluorescein staining score in the study eye
- *BASELINE_EDS* is the baseline pre-CAE® eye dryness score
- *CHANGE_ICSS* is the pre-CAE® inferior fluorescein staining in the study eye at Visit 5 (Day 85 ± 2) – *BASELINE_ICSS*
- *OUTLS* is the name of the output dataset that contains the statistical results for the treatment means from the ANCOVA model
- *OUTDIFFS* is the name of the output dataset that contains the statistical results for the differences in treatment means from the ANCOVA model

T-tests and Wilcoxon rank sum tests will also be conducted as sensitivity analyses to assess robustness of the results.

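### SAP Section 15 tests the treatment effect separately inside each subgroup but never estimates or tests whether it differs between subgroups

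*SAP*

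**What the plan says.** Protocol Section 12.4.9 names the subgroups but no method: "Subgroup analyses are planned for the 4 groups defined by the 2 stratification factors", that is, inferior corneal staining (at most 1.5, above 1.5) crossed with eye dryness (below 60, 60 or more).

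SAP Section 15 repeats the four cells for corneal staining on both scales, VAS and Total OSDI. It adds two further sets:

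- Halves split at the median pre-CAE baseline score: "These subgroup analyses will be conducted for all efficacy endpoints".
- Two groups for symptom endpoints, split at 20 minutes, the second being "Patients with time to CAE qualification > 20 minutes".

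The inference is then defined within subgroups: "For each subgroup, pairwise two-sample t-tests will be employed to compare treatment and vehicle means at each visit and time point". Wilcoxon tests are added. For change scores, "Changes from baseline will be compared between treatment groups using ANCOVA models that adjust for baseline value". Each comparison comes with a difference in means, a 95% confidence interval and a p-value, in the mITT population with observed data. SAP Section 20 lists the subgroup tables for Stage 1, Stage 2 and both stages combined.

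The primary model in SAP Section 13.1.1 has no interaction term either: "MODEL CHANGE_ICSS = BASELINE_ICSS BASELINE_EDS TREATMENT". No heterogeneity test or estimate of a difference in effects appears in the subgroup sections or in the models of SAP Section 13.1.

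**The concern.** A subgroup analysis asks whether the effect differs between groups of patients. Significance in one subgroup and not in another does not answer that, because each subgroup has far less power than the whole comparison. A uniform effect can easily cross 0.05 in some subgroups and miss it in others.

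The reader of the tables is left with that pattern and no direct measure of the difference. The question is a natural one here: the protocol sets 50% recruitment targets on both stratification factors, and Section 6.2 names enrichment on staining and dryness as part of the design rationale. SAP Section 20 also places tables marked Stage 1 in the interim package, and that includes the Stage 1 subgroup tables. The Data Review Committee would therefore see them.

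**Working it through.** **Inputs.** Difference 0.35, SD 0.75, dropout 10%, 93 active and 60 vehicle for 80% power (Protocol Section 12.1, SAP Section 5). Two-sided alpha 0.05 (SAP Section 8.4). The reference drug's difference of 0.25 (same sample size sections) serves as a lower effect.

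**Assumptions not in the documents.** Subgroups of equal size (Protocol Section 7.1 gives only two marginal 50% targets, so 25% per cell needs independent factors). SD 0.75 inside each subgroup. A t-test on change in inferior corneal staining, as in the sample size section. The same true effect everywhere.

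**The plan's own figure.** Noncentrality = 0.35 / (0.75 × √(1/93 + 1/60)) = 0.35 / 0.1242 = 2.818. The noncentral t with 151 degrees of freedom gives 80.0% power, as stated. The sizes are the post-dropout minima: 103 × 0.9 = 92.7 and 67 × 0.9 = 60.3.

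**Power inside a subgroup.** Splitting both arms into k equal parts divides the noncentrality by √k.

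- Halves (46.5 against 30): 2.818/√2 = 1.993, critical value 1.992, power 50.3%.
- Cells (23.25 against 15): 2.818/2 = 1.409, critical value 2.028, power 27.9%.

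**Chance of a mixed picture.** With disjoint subgroups and power p in each, P(some but not all significant) = 1 − p^k − (1 − p)^k.

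- Halves: 1 − 0.503² − 0.497² = 0.50.
- Cells: 1 − 0.2787⁴ − 0.7213⁴ = 1 − 0.006 − 0.271 = 0.72. All four cells are significant in only 0.6% of trials.

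**Range.** Same formulas, sizes after 10% dropout:

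| Data | Active / vehicle | Effect | Mixed, halves | Mixed, four cells |
|---|---|---|---|---|
| Combined, minimum | 93 / 60 | 0.35 | 50% | 72% |
| Combined, maximum, matching vehicle | 101.7 / 69.3 | 0.35 | 49% | 76% |
| Combined, maximum, pooled vehicle | 101.7 / 96.3 | 0.35 | 47% | 82% |
| Stage 1, maximum | 47.7 / 42.3 | 0.35 | 44% | 55% |
| Stage 2, 30 vehicle | 54 / 27 | 0.35 | 40% | 49% |
| Stage 2, 60 vehicle | 54 / 54 | 0.35 | 48% | 62% |
| Combined, minimum | 93 / 60 | 0.25 | 41% | 51% |
| Stage 2, 30 vehicle | 54 / 27 | 0.25 | 27% | 35% |

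Unequal two-way splits barely matter: at 93/60 and 0.35 the mixed rate is 51% for a 60:40 split and 55% for 70:30.

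**With an interaction test.** In simulation (200,000 trials per setting, uniform effect 0.35), an F-test for treatment by subgroup rejected in 4.9% to 5.1% of trials, for two and for four subgroups. At 93/60, among trials with a significant overall result, the mixed picture appeared in 58% (halves) and 83% (cells).

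**What that test can detect.** The difference between two halves' effects has standard error 0.75 × √(2 × (1/46.5 + 1/30)) = 0.248. A true difference of 0.35 gives 0.35/0.248 = 1.41 and about 29% power; about 80% is reached only at 0.70.

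**The case against.** The strongest reply is that nothing in the plan acts on these p-values. SAP Section 8.5 calls all efficacy analyses exploratory. The only documented adaptation concerns dose groups, for safety, tolerability or futility, and the choice of Stage 2 groups and numbers. A reader might infer that the within-subgroup tests will steer later enrichment, or select a subgroup by chance. The documents contain no rule to that effect, so this part of the objection stands in full.

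Several narrower points also stand:

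- Section 15 already requires differences with confidence intervals in every subgroup, which permits a rough comparison by eye.
- Very small groups, down to about 7 vehicle patients, belong to the four cells. Median halves in the combined data have about 46 and 30 patients, and the sizes of the CAE-qualification groups are not given.
- The effect and SD apply to inferior corneal staining. The documents give neither for VAS, OSDI or the other endpoints in the median splits.
- An interaction test has low power here, so a non-significant result would not show that effects are equal.
- Removing within-subgroup p-values altogether would be a reporting preference.

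None of this supplies the missing quantity. The exploratory label excuses unadjusted alpha, but it does not make a set of within-subgroup tests answer a question about differences. SAP Section 1 allows supplementary analyses, but one added after the data are seen is not pre-specified.

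**Conclusion.** The point holds as a cheap improvement to the plan. At the design effect, with an identical true effect in every subgroup, a mixed pattern of significance is about as likely as not for halves (50%) and is the usual outcome for four cells (72%) in the combined data. In Stage 2 at 54/27 the figures are 40% and 49%.

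The full range of about 27% to 82% matters. Its top end pools vehicle across dosing frequencies, whereas the SAP compares at matched frequency; with the matching vehicle group at its maximum the four-cell figure is 76%. Its bottom end takes the 0.25 effect in the smallest Stage 2 configuration. All figures rest on equal subgroups, SD 0.75 within each, 10% dropout and one endpoint. A smaller SD within baseline strata or after covariate adjustment would raise subgroup power and change the rates.

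The consequence is misreading of the subgroup tables, not a biased decision built into the trial.

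**What to change.** In SAP Section 15, for each active-vehicle comparison and each stage set:

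- Add to the mITT observed-data ANCOVA the subgroup main effect and a treatment-by-subgroup term, for each of the two stratification factors and for the CAE-qualification group.
- Alongside the median splits, fit a treatment-by-continuous-baseline term.
- Report the interaction estimate with its 95% confidence interval and p-value, with the estimate and interval leading.
- Keep the planned subgroup differences with confidence intervals, and state that within-subgroup p-values are not evidence of a differential effect.

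This needs no new data or patients, only a little programming and some extra table rows. The drawback is imprecision: between halves at 93/60 the 95% interval would extend about 1.976 × 0.248 = 0.49 units either side, wider than the 0.35 design effect. That limit is better shown than left implicit.

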4.1 Method of Assigning Subjects to Treatment Groups

Prior to initiation of study run-in (at Visit 1), each subject who qualifies for entry will be assigned a screening number. All screening numbers will be assigned in strict numerical sequence at a site and no numbers will be skipped or omitted. If all inclusion and exclusion criteria are met at Visits 1 and 2, each qualifying subject will then be assigned a randomization number at the end of Visit 2.

A randomization schedule will be provided to each investigational site. The randomization schedule will use block randomization stratified by site, such that there will be an approximate equal number of subjects assigned to each of the two treatment arms at each site for the Stage 1, Expansion Cohort. For Stage 1, Cohorts 1-3 patients with signs and symptoms of DED will be randomly assigned in a 4:1 ratio to receive either a single concentration of AXR-159 Ophthalmic Solution or AXR-159 Ophthalmic Solution Vehicle. The site staff will dispense to the patient the study kit labelled with the corresponding randomization number. The randomization number will be recorded on the patient's source document and eCRF. New kits will be dispensed at Visits 2, 3, and 4 based on the subject's randomization. The Sponsor, Investigators, and study staff will be masked during the randomization process and throughout the study.

During the run-in period, the patients will all be supplied with AXR-159 Ophthalmic Solution Vehicle. Patients will be informed that they will receive only vehicle during the 2-week run-in period. Following the run-in period the patient, site personnel, the sponsor and patients will be masked to the treatment

assignment for the 3 month treatment period. All study medication will be provided in identical unit of dose vials and cartons to maintain masking of the study.

For both Stages 1 and 2, patients with signs and symptoms of DED will be randomly assigned in a 4:1 (Stage 1, Cohorts 1-3) ratio, a 1:1 (Stage 1, Expansion Cohort) ratio, or to a 2:2:2:2:1:1:1 (Stage 2) ratio to receive either a single concentration of AXR-159 Ophthalmic Solution or AXR-159 Ophthalmic Solution Vehicle. For the expansion cohort in Stage 1 and Stage 2, subjects will be randomized by strata as follows:

- Site
- Baseline eye dryness score ≥ 60 , < 60
- Baseline inferior corneal staining > 1.5 , ≤ 1.5

Subjects will not be stratified in Cohorts 1, 2 and 3 in Stage 1.

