13.2.1 UNANESTHETIZED SCHIRMER'S TEST

Unanesthetized Schirmer's Test will be assessed on both eyes at all visits. Visit 1 and 5 assessments will be pre-CAE®. The Schirmer's test strip will be placed in the lower temporal lid margin of each eye. After 5 minutes, the test strip will be removed and the length of the moistened area will be recorded in millimeters (mm) for each eye. Lower values indicate less tears produced in the eye.

Unanesthetized Schirmer's Test will be summarized by treatment group and visit using quantitative summary statistics. Change from baseline will be also summarized.

Pairwise two-sample t-tests will be employed to compare treatment and vehicle means at each visit and time point. The differences in means, two-sided 95% CIs for the difference in means and p-values will be reported. Wilcoxon rank sum tests will also be conducted. Analyses will be performed on the mITT population with observed data only.

Changes from baseline will be compared between treatment groups using ANCOVA models that adjust for baseline value, baseline inferior corneal staining (Ora Calibra® scale) and baseline eye dryness (VAS). The differences in means, two-sided 95% CIs for the difference in means and p-values will be reported. T-tests and Wilcoxon rank sum tests will also be conducted. Analyses will be performed on the mITT population with observed data only.

Binary clinical cure variables will be defined by visit for Schirmer's test ≥ 5 mm, Schirmer's test ≥ 10 mm and Schirmer's change from baseline ≥ 5 mm, and will summarized by visit using number of subjects, frequency counts and percentages. Treatment groups will be compared pairwise with vehicle using Pearson's chi-square test or Fisher's exact test if the expected cell count is less than 5 in 25% or more of the cells. In addition, the proportion of responders will be compared between treatment groups using the Cochran-Mantel-Haenszel method stratifying by baseline ICSS (≤ 1.5 , > 1.5) and baseline eye dryness (< 60 , ≥ 60). For the Cochran-Mantel-Haenszel analysis of the combined Stage 1 and Stage 2 data, the study Stage will also be included as a stratification factor.

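### The median-split and CAE-qualification subgroup ANCOVAs leave out baseline inferior staining and eye dryness, which every other ANCOVA in the SAP carries, at a modest cost in precision

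*SAP*

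**What the plan says.** The primary model in SAP 13.1.1 states that "the ANCOVA model will include terms for baseline inferior corneal staining score (ICCS) and baseline eye dryness score as covariates". Sections 13.1.2 to 13.1.5 keep both scores and add the endpoint's own baseline where it differs. The ANCOVAs in section 13.2 are "ANCOVA models that adjust for baseline value, baseline inferior corneal staining (Ora Calibra® scale) and baseline eye dryness (VAS"). Protocol 12.4.5 and 12.4.6 say the same for the primary and continuous secondary endpoints.

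On randomisation, SAP 4.1 says "For the expansion cohort in Stage 1 and Stage 2, subjects will be randomized by strata as follows": site, eye dryness (cut at 60) and inferior staining (cut at 1.5). It adds "Subjects will not be stratified in Cohorts 1, 2 and 3 in Stage 1".

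SAP section 15 sets up three families of subgroups:

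- "Subgroup analyses are planned for the 4 groups defined by the 2 stratification factors", for the staining, VAS and OSDI endpoints.
- "Additional subgroup analyses will be conducted based upon strata defined by median baseline values in pre-CAE assessments", for all efficacy endpoints.
- "Subgroup analyses of symptom endpoints will also be conducted for the following two groups": time to CAE qualification up to 20 minutes, or longer.

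One ANCOVA sentence covers all three: "Changes from baseline will be compared between treatment groups using ANCOVA models that adjust for baseline value". In section 15 it ends there, so the baseline value is the only covariate. Protocol 12.4.9 lists the four cells but gives no model.

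**The concern.** The two scores were thought important enough to stratify on and to put in every other model. They are already collected, and they drop out without explanation in the analyses with fewer patients. A median split on, say, Schirmer or TFBUT does not fix staining or dryness, so both remain available to explain residual variance. If they are prognostic, the subgroup standard errors are larger than they need be.

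The scope is wide in tables, though not in consequence. By the titles in SAP section 20 there are 4 table families for the four cells, 13 for the median splits and 6 for CAE-qualification time. So 19 of 23 families (57 of 69 tables, at three per family) are of the second and third kind.

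**Working it through.** **Inputs.** SAP section 5 gives Stage 1 arms of 43–53 active and 37–47 vehicle, Stage 2 arms of 60 and 30–60, a difference of 0.35, SD 0.75, 10% dropout and two-sided 0.05. Protocol 6.1 gives 45 per group for the first expansion cohort, so a half is about 22 per arm. The share of residual variance that the two scores explain jointly, given own baseline (partial R²), is not in the documents. It is assumed here, over 0 to 0.20.

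**The plan's own figure.** With 93 and 60 evaluable, SE = 0.75 × √(1/93 + 1/60) = 0.124, and 0.35/0.124 = 2.82. Power is Φ(2.82 − 1.96) ≈ 80.5%, or 80.0% by noncentral t. Dropout also checks: 103 × 0.9 = 92.7 and 67 × 0.9 = 60.3. The stated 80% reproduces. It concerns the whole sample; the plan gives no power for subgroups.

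**Cost and gain of two more covariates.** With p covariates and N patients, chance imbalance inflates the variance by (N − 3)/(N − p − 3). Going from one covariate to three multiplies it by (N − 4)/(N − 6), and the residual variance falls by (1 − R²). So

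SE ratio = √[(1 − R²)(N − 4)/(N − 6)].

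For N = 44 the factor is 40/38 = 1.053, and break-even is R² = 1 − 38/40 = 0.05. The table gives SE with both scores divided by SE with own baseline only.

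| Half-sample | R² 0 | 0.05 | 0.10 | 0.20 |
|---|---|---|---|---|
| Formula, N = 44 | 1.026 | 1.000 | 0.973 | 0.918 |
| Simulation: 90 patients stratified as a whole, then cut at the own-baseline median | 1.02 | 1.00 | 0.97 | 0.93 |
| Same design, own baseline correlated 0.3 with the factors | 1.02 | 0.99 | 0.97 | 0.91 |
| Simulation: allocation balanced inside the 22-per-arm subgroup | 1.010 | 0.985 | 0.956 | 0.901 |
| Simulation: Stage 1 half, upper-end arms, subgroup unrelated to strata | 0.294/0.290 = 1.014 | – | 0.280/0.290 = 0.966 | 0.264/0.291 = 0.907 |
| Same, Stage 2 half (30 vs 15) | 1.018 | – | 0.965 | 0.910 |
| Same, combined-stage half | 1.008 | – | 0.956 | 0.901 |

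The formula assumes simple randomisation. Stratified balance makes the simulated cost at R² = 0 a little lower, about 1–2%. In the Stage 1 half with upper-end arms, at R² = 0.20, power for 0.35 units goes from 35% to 41%.

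**Calibration of the stated model.** At R² = 0.20, model versus empirical SE (in SD units) is 0.291 vs 0.287 in Stage 1 halves, 0.326 vs 0.313 in Stage 2 halves and 0.212 vs 0.201 in combined halves. The model SE is therefore 1–5% too large. Type I error is 4.7%, 4.1% and 4.4% respectively. Simulations that stratify the whole trial and then cut own-baseline halves give 4.3–5.2%.

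**The four cells.** Taking a quarter of each arm gives about 13 vs 12 in Stage 1 and 15 vs 8 in Stage 2. The variance factors are 21/19 = 1.105 and 19/17 = 1.118, so break-even R² is about 0.10 (1 − 19/21 = 0.095; 1 − 17/19 = 0.105). Only within-cell variation of the continuous scores is left to adjust for, about 36% of the full variance if the scores are normal and cut at the median. In Stage 1 cells the simulated SE goes from 0.409 to 0.430 at R² = 0 and from 0.382 to 0.383 at 0.20 (R² here is the full-population value). The own-baseline SE is calibrated there: 0.382 model versus 0.381 empirical at 0.20.

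**The case against.** The case for leaving section 15 alone has real substance.

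- **A short model is defensible in small subgroups.** This stands for the four cells. Each dichotomised factor is constant there by definition, and two covariates cost more than they return unless the scores predict well within the cell. In the half-samples the same argument carries only a 1–2% cost in SE.
- **The gain rests on an assumed R².** This stands. Once own baseline is in the model the extra R² may be small, and at 0.05 the gain is roughly nil.
- **Nothing is decided by these analyses.** This stands. SAP 8.5 calls all efficacy analyses exploratory, and no subgroup is powered.
- **The omission is not clean.** For inferior staining and eye dryness one of the scores is already the baseline value. Site, the third stratifier, is in no ANCOVA. The other models use the continuous scores, not the randomisation categories. Stage 1 Cohorts 1–3 were not stratified. All of this is correct and limits the point.

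A reader might go further and infer three things that the documents do not support:

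- **That the error bars are materially conservative, most of all in the smallest samples.** The smallest samples are the four cells, where the stated model is calibrated. In the halves, a type I error as low as 3.4% appears only if allocation is simulated as balanced inside the subgroup. The plan balances within strata of the whole sample and cuts the subgroups afterwards, which dilutes the effect.
- **That subgroup and overall effects will differ because the model changed.** Under randomisation both linear models target the same treatment difference. In simulation the two estimates differed on average by 0.003 SD or less. The unadjusted t-tests and Wilcoxon tests in sections 13.2 and 15 also allow a like-for-like comparison.
- **That section 15 contradicts the protocol, given the no-changes statement in SAP section 18.** Protocol 12.4.9 names no model for the subgroups, so there is nothing to contradict.

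**Conclusion.** The point holds as a cheap improvement, limited to the baseline-median and CAE-qualification-time subgroups. Their ANCOVA omits two prognostic candidates that every other ANCOVA in the SAP carries, and no reason is stated. The size is modest. Across an assumed partial R² of 0 to 0.20, the SE in a Stage 1 half with both scores added runs from about 2% larger to about 7–10% smaller, with break-even near 0.05. Stage 2 and combined halves behave alike. The stated model is unbiased, with type I error of about 4–5%.

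This rests on the assumed R², on halves of about 22 to 26 per arm in Stage 1, on roughly normal scores cut near their medians, and on subgroup membership that is unrelated or only moderately related to the two scores.

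**What to change.** In SAP section 15, state that the ANCOVAs for the baseline-median and CAE-qualification-time subgroups use the section 13.2 covariate set: the endpoint's own baseline, inferior corneal staining on the Ora Calibra scale, and VAS eye dryness. Where the endpoint is one of those two scores, it enters once. Keep the own-baseline model for the four staining-by-dryness cells, and say that the dichotomised stratification factors are fixed there by the subgroup definition. If the sponsor prefers the shorter model throughout, one sentence giving the reason would also settle the point.

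The cost is a line of text and two covariates already present in the section 13.2 models. The statistical downside is two error degrees of freedom, about 1–2% in the SE of a half-sample if the scores carry no information.
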